ACQ-6 = asthma control questionnaire-6; AE = adverse event; anti-HBc = hepatitis B core antibody; anti-HBs = hepatitis B surface antibody; BD = bronchodilator; CRS = chronic rhinosinusitis; ECG = electrocardiogram; EDN = eosinophil derived neurotoxin; FeNO = fractional exhaled nitric oxide; FSH = follicle-stimulating hormone; HbA1c = haemoglobin A1c; HBsAg = hepatitis B surface antigen; HIV = human immunodeficiency virus; HRT = hormone replacement therapy; ICF = informed consent form; IgE = immunoglobulin E; IGRA = interferon gamma release assay; NT-proBNP = N-terminal prohormone of B-type natriuretic peptide; SAE = serious adverse event; SARS-CoV-2 = severe acute respiratory syndrome coronavirus 2; SGRQ = St George’s respiratory questionnaire; SID = subject identification; SNOT-22 = sino-nasal outcome test-22; CCI SOC = standard of care; SV = study visit; TB = tuberculosis; VAS = visual analogue scale.

Table 2 Schedule of Activities: Study Intervention and Follow-up Periods

Period	Study Intervention							Follow-up		
Visit Number	SV4 (Randomisation)	SV5 (TC)	SV6	SV7	SV8	SV9	SV10	SV11	SV12	E/D
Study Day	1	2	8 (± 3)	29 (± 3)	57 (± 3)	85 (± 3)	113 (± 3)	141 (± 3)	169 (± 3)	
Study Week	0	0	1	4	8	12	16	20	24	
Efficacy assessments										
ACQ-6	X		X	X	X	X	X		X	X
SGRQ	X			X		X	X		X	X
SNOT-22 (comorbid CRS participants only)	X		X	X	X	X	X			
At-home eDiary completion and spirometry use	Twice daily throughout the intervention period.									
Assess adherence to at-home eDiary completion, spirometry, and SOC medication use	X	X	X	X	X	X	X	X	X	
Assessment of asthma exacerbations	X	X	X	X	X	X	X	X	X	X
PGI-BR							X			
Study participant feedback questionnaire (optional)	X						X		X	X
FeNO	X		X	X	X	X	X	X	X	X
Airwave oscillometry (pre-administration of study intervention)	X		X	X	X	X	X			
Airwave oscillometry (4 hours post-administration of study intervention)	X ^a									

Table 2 Schedule of Activities: Study Intervention and Follow-up Periods

Period	Study Intervention							Follow-up		
Visit Number	SV4 (Randomisation)	SV5 (TC)	SV6	SV7	SV8	SV9	SV10	SV11	SV12	E/D
Study Day	1	2	8 (± 3)	29 (± 3)	57 (± 3)	85 (± 3)	113 (± 3)	141 (± 3)	169 (± 3)	
Study Week	0	0	1	4	8	12	16	20	24	
In-clinic spirometry (pre-BD) (pre-administration of study intervention)	X		X	X	X	X	X	X	X	X
In-clinic spirometry (4 hours post-administration of study intervention)	X ^a									
In-clinic spirometry (post-BD)	X				X		X			
Safety assessments										
Concomitant medications	X	X	X	X	X	X	X	X	X	X

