 - Start date of systemic corticosteroids or temporary increase in a stable OCS background dose.
 - Date of emergency room or urgent care visits requiring systemic corticosteroids.
 - Date of hospital admission due to asthma.
- The end date of an exacerbation is defined as the latest of the following:
 - Last date of systemic corticosteroids or temporary increase in a stable OCS background dose.
 - Date of discharge from emergency room or urgent care visit.
 - Date of hospital discharge.

- If less than 7 days have elapsed since the end date of an asthma exacerbation and the start date of a new asthma exacerbation, the second event will be considered a relapse of the prior asthma exacerbation in the statistical analysis.
- All asthma exacerbations that occur during the treatment period and follow-up, must be recorded in the exacerbation eCRF. See Section 8.3.6 for additional information on recording asthma exacerbations as an AE/SAE during the study.

eDiary data and Exacerbations

Any sustained increase in asthma symptoms as reported via the eDiary (that do not meet the definition of criteria of an asthma exacerbation) will be graded as a worsening of asthma.

Specifically:

- An increase in rescue medication use of 4 or more puffs on at least 2 consecutive days compared with the average use during baseline or use of 12 puffs/day on any one day, and/or
- An additional nebulised β_2 agonist use on at least 2 consecutive days compared with the average use during baseline, and/or
- An increase of 2 or more nights with awakenings due to asthma requiring rescue medication over a 7-day period compared with the average during baseline, and/or
- ≥ 6 out of previous 7 nights with awakenings due to asthma requiring rescue medication

Alerts to study site will be triggered for participants who experience a drop in PEF $\geq 30\%$ on 2 consecutive days.

If an asthma exacerbation event is not associated with at least one of the above eDiary data deterioration criteria, the investigator will have to justify the decision for defining the event as an exacerbation and record it in the eCRF. Events that are not supported by any objective assessment will be deemed not to be a protocol-defined exacerbation.

Participants will be required to keep a record of their asthma symptoms in the eDiary as per the SOA (Table 1 and Table 2). The data captured in the eDiary will also be used to determine individuals CompEx events.

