3.4.6 Asthma CompEx

Asthma CompEx is a combination of exacerbations of asthma and diary events (ie, combination of eDiary variables). Asthma CompEx is a composite surrogate endpoint for exacerbations of asthma, recently developed by AstraZeneca (it is not yet a regulatory-approved clinical endpoint).

Diary events are defined by the threshold and slope criteria using the following morning/evening (AM/PM) diary variables:

- PEF (variable 1=V1= morning PEF; variable 2=V2= evening PEF).
- Symptom score (0 – 3) (variable 5=V5= morning symptom score; variable 6=V6= evening symptom score).
- Use of rescue medication (variable 3=V3= morning rescue medication usage; variable 4=V4= evening rescue medication usage).

A subject will be considered to have a CompEx event if the subject has one or both of the following:

- 1 An asthma exacerbation,
- 2 A diary event, which is defined as either the threshold criterion or the slope criterion (or both), as defined below, being met for ≥ 2 consecutive days.

For this purpose, “2 consecutive days” means strictly the same 2 consecutive days when assessing multiple requirements within those days. For the eDiary data (which is captured twice during the day), one day will be defined by the morning/evening pairing for consistency with published precedent for the CompEx endpoint. (Note: other eDiary endpoints in this trial will use an evening/morning pairing to define one day.) The morning eDiary recordings captured on the first day of treatment will not be included in the calculation of the CompEx endpoint.

Threshold criterion:

- (a) $\geq 15\%$ decrease from baseline in either morning (V1) or evening home-based PEF (V2),
and at least one of the following:
- (b) ≥ 1.5 doses increase from baseline in rescue medication in either the morning (for preceding night, V3) or evening (for preceding day, V4),
- (c) ≥ 1 score increase from baseline, or the absolute maximal symptom score, in either the morning (V5) or evening (V6).

For (b), the number of doses of rescue medication is defined as the number of puffs of inhaler recorded in the morning and evening, respectively.

For (c), the asthma symptom score (scored 0-3) as described in Section 3.6.2.1 (V1-V6), provided those non-missing values meet the criterion.

Slope criterion:

One of (a), (b) or (c) above is met for ≥ 2 consecutive days *and* the regression slope requirement over the preceding 5 days is also met.

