The regression slope requirement in the preceding 5 days is that all of the following are met:

- Morning PEF slope $\leq -3\%/day$;
- Evening PEF slope $\leq -3\%/day$;
- Morning (preceding night) rescue medication slope ≥ 0.3 doses/day;
- Evening (preceding day) rescue medication slope ≥ 0.3 doses/day;
- Morning asthma symptom score slope ≥ 0.2 score/day;
- Evening asthma symptom score slope ≥ 0.2 score/day.

In all of the above cases, the regression slope is the point estimate of the slope obtained from a linear regression of the absolute values of each of the six variables (V1-V6) separately against day number, with no other variables included in the regression model.

For morning and evening PEF, the regression slope thus obtained will first also be divided by the baseline PEF value before applying the above criterion. The following table shows how the timing for the 5-day requirement for the regression slopes fits with the 2-consecutive day requirement, where “Day 0” here refers to the first of the 2 consecutive days (shaded) to be used each time the rolling 2 consecutive day assessment is made:

Table 3 Timing for assessment of CompEx slope criterion

	Day -4	Day -3	Day -2	Day -1	Day 0	Day 1
Threshold (a), (b), (c)					x	x
Slope	x	x	x	x	x	x

A regression slope will be calculated provided there are at least two non-missing values in the required 5 days. If one or more of the six variables above (V1-V6) does not have at least two non-missing values in the required 5 days, then the slope requirement therefore cannot be met.

The start date of a CompEx event is defined as the earliest of the exacerbation or objective deterioration start dates which meets the definition. Diary event start date is defined as the earliest Day 0 (in notation from Table 15) from any series of rolling 2 consecutive days which first qualifies using either the threshold or slope criterion.

The end date of a CompEx event is defined as the latest of the exacerbation or objective deterioration end dates which meets the definition. Diary event end date is defined as the latest Day 1 (in notation from Table 3 – Timing for assessment of CompEx slope criterion) from any series of rolling 2 consecutive days which last qualifies using either the threshold or slope criterion.

The event duration is defined as the end date minus the start date plus 1.

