If the end date of the first CompEx event and the start date of the second CompEx event are less than 7 days apart for any subject, then these will be counted as one CompEx event.

For CompEx analyses, only on-treatment events (based on the period from baseline to last dose date +28 days) will be considered. A supplementary analysis including events in the period from baseline to end of follow-up (Week 24) will also be conducted.

Time-to-first event will be defined as: [Start date of first event or censoring – date of 1st dose] + 1.

Date of first event will be the first start date of a CompEx event as defined above. For participants who do not experience an on-treatment CompEx event, date of censoring will be the minimum between the date of last dose plus 28 days, and the last day of eDiary recording during the on-treatment period. For the analysis of CompEx during combined treatment and follow-up period, date of censoring will be the minimum between the date of end of study visit, and the last day of eDiary recording during combined treatment and follow-up period .

For recurrent events, there must be a gap of 7 days between events ie, at least 7 days between end date of first CompEx event and start date of second CompEx event. Events that occur closer in time will be collapsed into one event.

The time during the event and the 7 days after each event will not be considered when defining time at risk for the CompEx event rate. Time at risk will be defined as [Date of last treatment plus 28 days– date of 1st dose] + 1 – recovery time. For the analysis of CompEx during combined treatment and follow-up period, the time at risk will be defined as [date of end of study visit – date of 1st dose] + 1 – recovery time.

The annualised rate of asthma CompEx events, during intervention period (Baseline to last dose date +28 days) per participant will be calculated as:

Annualised rate of asthma CompEx events during intervention period =

Total number of asthma CompEx events

$$\frac{\text{Total number of asthma CompEx events}}{(\text{Date of last dose of IP} + 28 - \text{Date of the first dose of IP} - \text{recovery time} + 1)/365.25}$$

where the recovery time is defined as:

$$\sum_{i=1}^k [\min(i^{\text{th}} \text{ event end date} + 7, \text{date of last dose} + 28) - i^{\text{th}} \text{ event start date} + 1]$$

The annualised rate of asthma CompEx events, during intervention and follow-up periods (Baseline to Week 24) per participant will be calculated as:

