4.2.5.4 Analysis of Asthma CompEx

Time to first asthma CompEx event will be analysed using a Cox proportional hazard model, with group, background medication, geographic region and baseline ICS total daily dose as covariates (see Section 4.1.6). All available data from participants through Week 16 will be included. Additionally, the analysis of time to first asthma CompEx event will be repeated using all available data from participants through Week 24 (end of follow-up).

Time to first asthma CompEx will also be displayed in a Kaplan-Meier plot, including all data through to Week 24 (end of follow-up).

The asthma CompEx event rate will be analysed using negative binomial regression, with the log(follow-up time) included as an offset term and treatment group, geographic region, baseline ICS total daily dose as covariates (see Section 4.1.5). The dependent variable will be the number of asthma CompEx events through Week 16. All available data from participants through to Week 16 will be included, irrespective of whether they discontinued study intervention.

Additionally, the analyses of the asthma CompEx event rate will be repeated using all available data from participants through Week 24 (end of follow-up).

Asthma CompEx events will be also reported in listing for the ITT population.

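### Time to first CompEx event: event-free participants are censored at their last eDiary day but exacerbations after that day still count, which biases the Kaplan-Meier estimate downwards

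*SAP*

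**What the plan says.** **Events.** SAP 3.4.6: "A subject will be considered to have a CompEx event if the subject has one or both of the following", namely an asthma exacerbation or a diary event. An exacerbation therefore qualifies without any diary data. Exacerbations come from a separate source that does not stop with the diary. Protocol 8.1.5: "All asthma exacerbations that occur during the treatment period and follow-up, must be recorded in the exacerbation eCRF".

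**Event date.** SAP 3.4.6: "The start date of a CompEx event is defined as the earliest of the exacerbation or objective deterioration start dates which meets the definition", and for the time-to-event variable, "Date of first event will be the first start date of a CompEx event as defined above". Neither sentence limits the date to the period in which the diary was running.

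**Censoring.** Participants with no on-treatment event fall under this rule: "date of censoring will be the minimum between the date of last dose plus 28 days, and the last day of eDiary recording", counting on-treatment entries only. The combined treatment and follow-up analysis has its own version: "date of censoring will be the minimum between the date of end of study visit, and the last day of eDiary recording", again counting only entries made within its period.

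**Use.** SAP 4.2.5.4 plans Cox models through Week 16 (the secondary endpoint) and through Week 24 (supplementary), and a Kaplan-Meier plot that runs to Week 24.

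**When the eDiary ends.** The documents disagree.
- Protocol 1.3, Table 2, has eDiary completion and home spirometry "Twice daily throughout the intervention period". Protocol 4.1 lists diary completion under the intervention period only.
- The same Table 2 schedules checks of eDiary adherence at SV11 and SV12. Protocol Section 3 has home PEF and FEV1 endpoints up to Week 24. SAP 3.1.4 defines 2-weekly diary periods to Day 169. SAP 3.6.2 bases ePRO analyses on data to Week 24. The Week 24 censoring rule itself refers to diary recording in follow-up.

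**The concern.** Take two participants whose last diary entry is on Day 113. One has no event and is censored on Day 113. The other exacerbates on Day 140, stays in the risk set for 27 more days, and then counts as an event. Whether a person is treated as observed after the diary stops is decided by what happens to that person later. Kaplan-Meier and Cox methods need an observation period that does not depend on the future outcome.

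The effect is a denominator that is too small after diaries stop, while the numerator keeps all exacerbations. The event-free proportion is then too low. What is at stake is a secondary endpoint, its supplementary Week 24 analysis and its only survival figure. The primary endpoint and the testing hierarchy are not touched.

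**Working it through.** The documents give no CompEx event rate, event count or power, so there is no stated figure to reproduce. The check has three parts.

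**1. Hand example.** About 76 per arm (228/3, SAP 1.3). Assumed for illustration: 23 first events by Day 113, 4 first exacerbations between Days 114 and 169, all diaries ending on Day 113. That leaves 76 − 23 − 4 = 49 without an event. S(t) is the product of (1 − events/at risk).

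- At Day 113, under any rule: S = 53/76 = 0.697.
- Written rule: 49 are censored on Day 113 and 4 remain, all future events. S(169) = 0.697 × 3/4 × 2/3 × 1/2 × 0/1 = 0.
- Rule (i), everyone stops at the last diary day: S = 53/76 = 0.697, which is really a Day 113 figure.
- Rule (ii), everyone followed to end of study: S(169) = 53/76 × 52/53 × 51/52 × 50/51 × 49/50 = 49/76 = 0.645.

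**2. Simulation of the event-free proportion.** 76 per arm, 2000 runs per row. Assumptions, none from the documents: diary-type events 1.0 per year; exacerbations 0.25, 0.5 or 1.0 per year; early diary lapse 10% or 30%. Each cell gives the three exacerbation rates in that order.

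| Setting | Written rule | Rule (i) | Rule (ii) | Written below (i) by |
|---|---|---|---|---|
| Week 24, diary ends Day 113, 10% lapse | 0.087 / 0.019 / 0.001 | 0.669 / 0.622 / 0.531 | 0.658 / 0.590 / 0.467 | 0.58 / 0.60 / 0.53 |
| Week 24, diary to Day 169, 10% lapse | 0.553 / 0.487 / 0.382 | 0.556 / 0.492 / 0.391 | 0.570 / 0.505 / 0.401 | 0.003 / 0.005 / 0.009 |
| Week 24, diary to Day 169, 30% lapse | 0.543 / 0.472 / 0.358 | 0.555 / 0.492 / 0.387 | 0.599 / 0.531 / 0.419 | 0.012 / 0.020 / 0.029 |
| Week 16, 10% lapse | 0.671 / 0.618 / 0.523 | 0.673 / 0.623 / 0.531 | 0.684 / 0.633 / 0.540 | 0.002 / 0.005 / 0.008 |
| Week 16, 30% lapse | 0.663 / 0.606 / 0.500 | 0.672 / 0.623 / 0.527 | 0.706 / 0.654 / 0.554 | 0.009 / 0.017 / 0.027 |

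In the first row the curve reached exactly zero in 87%, 97% and 99.8% of arms, on a mean of only 2.2, 4.0 and 6.6 post-diary events per arm. Twenty days before Week 24, everyone still at risk was a future event. With diaries to Week 24 that share was 7% to 13%, and the curve reached zero in at most 0.25% of arms. In the Week 16 rows the share was also 7% to 13%, and zero was reached in at most 0.1%.

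**3. Hazard ratio.** A separate simulation used 72 per arm, CompEx rates of 1.0 to 2.5 per year (40% exacerbations) and a true hazard ratio of 0.60. With diaries ending at Week 16, the Week 24 estimate was about 0.03 nearer to 1 (for example 0.63 against 0.605). On the log scale that is ln(0.63/0.605) = 0.04. Expected first events by Week 24 are 72 × (1 − exp(−rate × 168/365.25)), or 27 to 49 on placebo; with the rate multiplied by 0.60 they are 17 to 36 on active. The standard error √(1/d₀ + 1/d₁), with d₀ and d₁ those two counts, is then 0.31 to 0.22, so the shift is 0.13 to 0.18 standard errors. With diaries to Week 24 and 15% lapse the hazard ratio was almost unchanged.

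**The case against.** **The SAP plans on diaries to Week 24.** The adherence checks, the home endpoints, the 2-weekly periods and the wording of the Week 24 censoring rule all point that way. This stands as a limit on size. A reader might infer that late risk sets always consist only of people about to have an event, or that the Week 24 curve must fall to zero. The documents do not support that. It follows only once every event-free participant's diary has stopped, which needs the Table 2 row to be the operative one.

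**The secondary endpoint is hardly affected.** Dosing visits run to SV9, Day 85 (SAP 3.5.2 with Protocol Table 2), so the on-treatment window closes near 85 + 28 = Day 113, about where even the shorter diary reading ends. Only early lapses matter there. This also stands: the large effect belongs to the supplementary Week 24 curve and should not be read across to the Week 16 result or to the hazard ratio.

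**The Week 24 sentence does not itself say that it applies only to event-free participants.** That restriction is in the preceding on-treatment sentence. Reading it across is natural, since the time variable runs to the first event or to censoring. If a cap on everyone was meant, the text needs to say so.

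**Stopping everyone at the last diary day has its own cost.** It drops confirmed exacerbations, and someone admitted to hospital the day after the last entry would be censored as event-free. This is a fair point. It is a reason to name the alternative rule, not to keep one that treats the two kinds of participant differently.

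**Conclusion.** The rule is wrong as written. Events and censoring use different ends of observation, so the Kaplan-Meier estimate is biased downwards. The direction does not depend on the assumed rates; the size does.

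- If diaries end at Week 16, the Week 24 Kaplan-Meier curve will usually fall to or near zero and cannot be interpreted. The hazard ratio moves only slightly, by about 0.03.
- If diaries run to Week 24, and in the Week 16 secondary analysis, the curve is too low by about 0.2 to 3 percentage points with 10% to 30% lapse, with little effect on the hazard ratio.

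These figures rest on assumed event and lapse rates and on lapse that is unrelated to outcome. The correction is worth making because it is cheap and because one planned figure could become meaningless.

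**What to change.** 1. State in the protocol and SAP when the eDiary ends, and reconcile the Table 2 row with the Week 24 endpoints, diary periods and adherence checks.
2. In SAP 3.4.6, define one observation end for every participant, with or without an event. Preferably this is the earlier of the analysis period end and the last eDiary day. Count a first CompEx event only if it starts on or before that date; otherwise censor there. Later exacerbations stay in the separate time-to-first-exacerbation analysis (SAP 4.2.6.3). If the diary ends at Week 16, the CompEx curve should stop there too.
3. The alternative is to follow everyone to the period end. This matches the time at risk that SAP 3.4.6 already uses for the CompEx event rate, which has no diary cap. Whichever rule is chosen, run the other as a sensitivity analysis.

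**Cost.** A sentence or two and one programming condition. The preferred rule loses a few late exacerbations from this analysis and differs from the event-rate follow-up. The alternative counts diary-free time as at risk although diary events cannot be seen in it. In the table, with diaries to Week 24 and 30% lapse, it puts the event-free proportion 0.599 − 0.555 = 0.044 above rule (i) at the lowest exacerbation rate.

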3.6.4 Asthma exacerbation

Asthma exacerbation will be assessed throughout the duration of the study.

Time to first asthma exacerbation will be calculated as start date of asthma exacerbation minus date of 1st dose plus 1.

The annualised rate of asthma exacerbation during intervention period (Baseline to last dose date +28 days) per participant will be calculated as:

Annualised exacerbation rate during intervention period =

$$\frac{\text{No. of exacerbations}}{(\text{Date of last dose of IP} + 28 - \text{Date of 1st dose} - \text{recovery time} + 1) / 365.25}$$

The annualised rate of hospitalised asthma exacerbation during intervention period per participant will be calculated as:

Annualised hospitalised exacerbation rate during intervention period =

$$\frac{\text{No. of exacerbations which resulted in hospitalisation}}{(\text{Date of last dose of IP} + 28 - \text{Date of 1st dose} - \text{recovery time} + 1) / 365.25}$$

The recovery time is defined as:

$$\sum_{i=1}^k [\min(i^{\text{th}} \text{ exacerbation end date} + 7, \text{date of last dose of study intervention} + 28) - i^{\text{th}} \text{ exacerbation start date} + 1]$$

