4.1.5 Negative binomial regression

Negative binomial regression will be used for the analysis of event rates. In this study the response variable in the model will be the number of asthma CompEx events, the number of asthma exacerbations, or the number of hospitalised asthma exacerbations experienced by a participant. The model will include treatment group, background medication, geographic region and baseline ICS total daily dose as covariates. The logarithm of the participant's corresponding follow-up time will be used as an offset variable in the model to adjust for participants having different exposure times during which the events occur.

The standard parameterization approach (NB2) of the negative binomial model will be applied using PROC GENMOD (SAS procedure).

The estimated annualised event rate in each group, the estimated treatment effect (ie, the rate ratio of each treatment group versus placebo), corresponding two-sided 80% CI, and one-sided p-value for the rate ratio will be presented. The estimate of the negative binomial overdispersion parameter will also be reported.

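### The intervention-period CompEx and exacerbation rates run time at risk to last dose + 28 days without ending it at study exit, and neither CompEx rate ends it at the last eDiary day

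*SAP*

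**What the plan says.** SAP 3.4.6 gives three end-of-observation rules for CompEx.

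- **Intervention-period rate.** "Time at risk will be defined as [Date of last treatment plus 28 days", minus the date of first dose, plus one, less recovery time. Recovery time is the only deduction: "The time during the event and the 7 days after each event will not be considered when defining time at risk".
- **Time to first event.** For participants without an on-treatment event, "date of censoring will be the minimum between the date of last dose plus 28 days, and the last day of eDiary recording" within the on-treatment period.
- **Week 24 rate.** "the time at risk will be defined as [date of end of study visit", again minus first dose, plus one, less recovery time. The matching Week 24 time-to-first-event rule does stop at the last eDiary day if that is earlier.

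SAP 3.6.4 ends the exacerbation and hospitalised-exacerbation denominators in the same way as the first rule: "The annualised rate of asthma exacerbation during intervention period (Baseline to last dose date +28 days) per participant will be calculated as" the count over last dose + 28 days minus first dose, less recovery time, plus one.

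On data sources, SAP 3.4.6 says "Asthma CompEx is a combination of exacerbations of asthma and diary events". Protocol 8.1.5 says that exacerbations during treatment and follow-up "must be recorded in the exacerbation eCRF".

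For the negative binomial model, SAP 4.1.5 says the logarithm of the participant's "corresponding follow-up time will be used as an offset variable in the model". SAP 4.2.5.4 also speaks of follow-up time. Neither section ties this term to the time at risk in 3.4.6 or 3.6.4.

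**The concern.** A rate needs a denominator covering the days on which an event could have been seen. Diary events are built from home PEF, symptom scores and rescue use, so they cannot be detected once the diary stops. No event of either kind is reliably observed after a participant leaves. Under the stated formulas those days still count as event-free.

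Each arm's annualised rate is then too low. If stopping differs between arms, the rate ratio moves in favour of the arm with more of it. The two CompEx analyses, both serving one secondary objective, could also disagree only because they use different observation periods.

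The time-to-first-event analysis has a related defect. The diary-stop censoring applies to participants without an event, while an eCRF exacerbation after diary stop still counts as a first event. Staying in the risk set beyond diary stop therefore depends on having an event later.

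**Working it through.** The plan gives no CompEx rate, dispersion or diary-stopping fraction, so there is no stated figure for this point to reproduce. (The FEV₁ sample size does reproduce, at 80.5% power with 72 per arm, but has no bearing here.)

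**Inputs from the documents.** SAP 3.5.2 places dosing at SV4, SV7, SV8 and SV9, which Protocol Table 2 schedules on Days 1, 29, 57 and 85. A full completer has 85 + 28 − 1 + 1 = 113 days, ending on Day 113 (Week 16).

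**Study exit, one participant.** Nobody is dosed after leaving, so the overcount is at most 28 days.
- Exit on the day of the dose at Day 29, 57 or 85: observed/counted = 29/57, 57/85 or 85/113, so that participant's rate is multiplied by 0.51, 0.67 or 0.75.
- Last dose Day 57, exit Day 64, one 5-day event with its 7 recovery days (12 days deducted): 365.25/(85 − 12) = 5.00 per year as written, and 365.25/(64 − 12) = 7.02 if cut at exit.
- Last dose Day 1, exit Day 8: (1 + 28) − 1 + 1 = 29 days on-treatment. If the end-of-study visit is on Day 8, the longer Week 24 analysis gives 8 − 1 + 1 = 8 days.

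**Study exit, one arm.** Assume 5% leave just after the Day 29 dose, which is the full 28-day overcount: (0.95×113 + 0.05×29)/(0.95×113 + 0.05×57) = 108.8/110.2 = 0.987. The arm's rate falls by about 1%.

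**Diary stop with dosing continued (CompEx only).** Let a fraction w stop on day d, and let q be the share of CompEx events that only the diary can detect. The arm's rate is multiplied by [113 − w·q·(113 − d)]/113. Under a true ratio of 1, the expected rate ratio is the quotient of the two arms' multipliers. Stopping is assumed unrelated to event risk.

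| Assumed stopping, active vs placebo | q = 1 | q = 0.5 |
|---|---|---|
| 20% vs 10%, Day 57 | 101.8/107.4 = 0.948 | 107.4/110.2 = 0.975 |
| 15% vs 5%, Day 29 | 100.4/108.8 = 0.923 | 106.7/110.9 = 0.962 |
| Equal in both arms | 1.000 | 1.000 |

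Swapping the arms inverts the ratio: 107.4/101.8 = 1.055 in the first row at q = 1. With 10% stopping at Day 57 in both arms, the ratio is unaffected but each arm's rate is still multiplied by 107.4/113 = 0.950 at q = 1.

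**Simulation.** A negative binomial model with a log-time offset was run with 76 per arm and 1,500 runs per scenario. Assumptions were a rate of 1.5 per year, dispersion 1, true ratio 1, and all events lost after diary stop.

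| Diary stop, placebo vs active | Ratio, as written | One-sided 10% error, as written | Ratio, cut at diary stop | Error, cut |
|---|---|---|---|---|
| 5% vs 20% | 0.930 | 15.7% | 1.003 | 9.7% |
| 10% vs 30% | 0.900 | 17.9% | 1.000 | 10.1% |

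**The case against.** The strongest reply is that the effect is small and rests on assumptions.

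- Participants who stop treatment are kept in the study (Protocol 7.1), and few withdrawals are anticipated (Protocol 7.2). Entry requires at least 70% eDiary adherence, and adherence is checked at study visits. Nothing in the documents points to a 10-point gap in diary stopping between arms. This stands: the fractions are illustrations.
- Someone who stops the diary but attends visits still has exacerbations recorded, so CompEx is only partly unobserved. This stands, and makes the q = 1 ratios upper bounds on the distortion in those scenarios.
- The offset is called follow-up time, so the program might already use observed time. This is possible. But the only explicit denominators are those in 3.4.6 and 3.6.4, so at best the SAP leaves it open.
- Ending CompEx counting at diary stop discards observed exacerbations and sits uneasily with the intention in 4.2.5.4 to use all data to Week 16. If severe worsening is what stops the diary, the cut removes those events. It also does nothing for intermittent gaps. This is a fair objection to using the cut alone, and is why a sensitivity analysis is needed.

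A reader might infer that diary stop also understates the exacerbation and hospitalised-exacerbation rates. The documents do not support that: those events come from the eCRF, so only study exit matters. A reader might also take the Day 8 leaver as proof of an impossible value. The 8 days assumes that the end-of-study visit is the exit date, which the SAP does not define for leavers; it is an inconsistency in one extreme case, not an arm-level effect.

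**Conclusion.** The gap is real on the text. Both intervention-period denominators continue past study exit, and both CompEx rates continue past the last eDiary day. The SAP's own censoring rule for time to first CompEx event already contains the missing diary cut.

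Study exit is a minor matter. Diary stop in the CompEx rate is the larger one: the null ratio moves to about 0.95 or 0.92 at worst in the two scenarios, and to about 0.97 or 0.96 if half of events are diary-only. These sizes depend on assumed stopping fractions and times, an assumed diary-only share, non-informative stopping, and the offset being the stated time at risk.

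It would go too far to say that the trial's ratio will favour MEDI3506: nothing in the documents shows which arm would stop more, or that the arms would differ. The primary conclusion is not touched either. The testing hierarchy in SAP 4.1.1 covers only FEV₁ at two doses; CompEx is secondary and the exacerbation rates are exploratory. The change should be made, but it is not critical.

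**What to change.** 1. In SAP 3.4.6 and 3.6.4, end time at risk, and the cap inside the recovery-time formula, at the earlier of the period end already chosen and the date of study withdrawal or death.
2. For the CompEx rate, in both the intervention-period and Week 24 analyses, also end time at risk and the recovery cap at the last eDiary day, matching the existing censoring date. Count events only to that date in both the rate and the Cox analyses, so that retention after diary stop does not depend on having an event. Report a sensitivity analysis that adds eCRF exacerbations after diary stop, with time at risk running to study exit within the period.
3. In SAP 4.1.5 and 4.2.5.4, state that the offset is the log of this time at risk.

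The cost is SAP wording, a changed derived end date and one sensitivity analysis; no new data are needed. The downside is that some exacerbations after diary stop leave the main CompEx count, although they remain in the exacerbation endpoint and the sensitivity analysis. The cut does not remove bias if stopping is itself related to event risk.
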